## Protocol

The protocol recommended tactile assessments of the adductor pollicis TOF count, if feasible, and intraoperative muscle relaxation according to surgical requirement. All rocuronium doses were calculated using ideal body weight (IBW). Previous studies indicate that NMBDs are more appropriately dosed based on IBW than on actual body weight, 12 and high BMI has been identified as a risk factor for PRNB.13 IBW was calculated by using the Devine formula as 50.0 + 0.9 kg cm-1 over 152 cm for males and 45.5 + 0.9 kg cm-1 over 152 cm for females, with intubation dose calculated as 0.6 mg kg-1 (IBW). Doses for women were reduced by 15%, as the ED95 is lower for females, leading to prolonged effects if given the same dose of rocuronium as males.14,15 We calculated an additional 1% dose reduction per year over 55 of age because of previous studies indicating a prolonged effect in older patients,15 with age being a known risk factor for PRNB.16 The protocol recommended avoiding deep block (complete absence of the TOF response) because there is conflicting evidence that deep block is of benefit.17 If there was a continued need for muscle relaxation, maintenance doses were recommended when the TOF count reached 3; each maintenance dose was calculated as 25% of the intubation dose rounded up to the next higher 5 mg, except during the last hour of the case when it was rounded down to the next lower 5 mg. At the end of the procedure, a tactile pre-reversal assessment of the thumb response to ulnar nerve stimulation was mandatory. If facial nerve stimulation and evaluation of eye-muscle twitches had been used intraoperatively, a change of monitoring site to ulnar nerve stimulation was conducted at the end of the procedure 18 to mitigate against eye-muscle monitoring as a significant risk factor for PRNB. 13 Reversal dose of neostigmine was calculated using ideal body weight (IBW) while the sugammadex dose was based on actual body weight. The protocol calls for a minimum of 10 minutes after neostigmine administration and minimum 3 minutes after sugammadex administration before tracheal extubation (Table 1).

Providers were trained regarding the implementation of the new protocol and instructed to follow the practice suggestions. The research staff assisted the providers with protocol reminders and dose calculations.

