## Study procedures

We had originally planned to use either acceleromyography (Stimpod 450, Xavant, Pretoria, South Africa) or electromyography for research measurements in this study. After trying electromyographic measurements for four patients in this study we observed that the new electromyographic monitors at our institutions had inconsistent performance. We therefore decided to exclusively use a Stimpod 450 acceleromyograph for all patients. This is a tri-axial acceleromyograph, and subsequently all measurements were obtained in the same manner for all patients. All measurements were normalized, as this is recommended when using acceleromyography.19 Two ECG surface electrodes were placed over the ulnar nerve at the wrist, with the positive electrode 3-4 cm proximal to the negative electrode. Immediately after induction of general anesthesia, and before any muscle relaxant had been administered, research staff obtained baseline TOFR measurements. The baseline and all other quantitative TOFR measurements were obtained by averaging two measurements separated by at least 15 s. If the initial two measurements were not within 10% agreement, additional measurements (up to four total) separated by at least 15 s were made and the two closest TOF ratios averaged. Anesthesia providers were blinded to all quantitative measurements. After baseline measurements, the research staff disconnected the Stimpod 450, but left the surface electrodes in place to be used for subsequent study measurements. Additional measurements were obtained in duplicate immediately before reversal when the anesthesia provider made the tactile pre-reversal assessment, immediately before tracheal extubation, and a final set of measurements were obtained within 5 min of arrival to the post anesthesia care unit (PACU).

Baseline measurements were used to normalize all subsequent measurements. This was done to correct for the inflated TOFR values that are usually obtained by acceleromyography. 20,21 As an example, if the baseline TOFR is 1.15 and the raw postoperative TOFR is 0.95, then the nTOFR is 0.95/1.15 =0.83. Normalization usually yields lower TOF ratios, and it is more likely to classify observations as positive for PRNB. Therefore, the incidence of PRNB is typically higher when comparing normalized to non-normalized (also referred to as "raw") measurements. PRNB was defined as a nTOFR <0.9 on arrival to the PACU.

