Study Title: Best Practice With Rocuronium, Neostigmine, Sugammadex, and Subjective Monitoring

NCT03543826

Document title: Statistical Analysis Plan

Date of the document: 5/8/2019

Statistical analysis

We present descriptive statistics [mean (standard deviation) or frequencies] for baseline measures of patient and surgery characteristics. The primary endpoint, incidence of PRNB (nTOFR <0.9) on arrival to the PACU, was calculated with exact binomial 95% confidence interval, and graphically displayed using scatterplots. The primary analysis was "per-protocol" and patients were excluded if the protocol was not followed. Secondary endpoints included severe PRNB, defined as nTOFR <0.7 on arrival to the PACU, and PRNB at time of tracheal extubation (nTOFR <0.9). These were also calculated with the exact confidence intervals. Additionally, we calculated the incidence of severe PRNB at time of tracheal extubation and the incidence of PRNB using raw (non-normalized) measurements.

We compared the duration between end of surgery and arrival to the PACU for patients whose tracheas were extubated in the OR and those extubated in PACU. We also compared the duration between end of surgery and arrival to the PACU for patients receiving sugammadex or neostigmine.

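### Does ending both duration comparisons at PACU arrival distort the comparison of sugammadex with neostigmine?

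*SAP*

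**What the plan says.** The SAP (Statistical analysis) ends with two duration comparisons on the same interval. The first is by place of extubation: "We compared the duration between end of surgery and arrival to the PACU for patients whose tracheas were extubated in the OR" against those extubated in the PACU. The second is by reversal agent: "We also compared the duration between end of surgery and arrival to the PACU for patients receiving sugammadex or neostigmine". It states no purpose for either, and no stratification or adjustment by place for the second.

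The protocol (section Protocol) sets a "minimum of 10 minutes after neostigmine administration and minimum 3 minutes after sugammadex administration before tracheal extubation". The waits therefore start at drug administration and end at extubation. Under Study procedures, research measurements are taken "immediately before tracheal extubation, and a final set of measurements were obtained within 5 min of arrival" in the PACU. That section does not say that the clock time of extubation was recorded.

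**The concern.** The protocol's waits end at extubation, while the SAP's clock ends at PACU arrival. For a patient extubated in the OR, the interval holds the whole wait after end of surgery plus transport. For a patient taken to the PACU still intubated, it can stop while the wait is running. The SAP itself shows that both groups exist: "patients whose tracheas were extubated in the OR and those extubated in PACU".

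If neostigmine patients, with the longer wait, were more often extubated in the PACU, some of their wait would fall outside the interval. The agent difference would then come out too small, and could even change sign. A reader who took the result as the time saved by sugammadex would be misled. The available text describes no randomisation to agent, so nothing guarantees equal PACU shares.

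**Working it through.** **What is being estimated.** The SAP defines its quantity by a start (end of surgery) and an end (PACU arrival). Every patient has both events wherever extubation happens. The preceding sentence of the SAP compares OR with PACU extubation on the same interval, so place of extubation was plainly in view. The natural reading is time to leaving the OR and reaching the PACU. A patient who travels intubated did leave earlier, and the interval correctly shows this. The available documents do not name the result as anything else.

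**How much wait could be left out.** The SAP gives no figure to reproduce. From the protocol come the two minimum waits, 10 and 3 minutes. Everything else here is assumed:
- reversal at end of surgery
- emergence time normal, mean 6, SD 2 minutes
- transport T = 5 minutes
- PACU-extubated patients leave the OR at L = 3, 5 or 7 minutes
- PACU-extubated shares pN (neostigmine) and pS (sugammadex)

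A patient is ready at the later of emergence and the minimum wait c. With z = (c − 6)/2, mean readiness is c·Φ(z) + 6·(1 − Φ(z)) + 2·φ(z). This gives wN = 10.02 minutes for neostigmine (c = 10) and wS = 6.06 for sugammadex (c = 3).

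Let R be the mean wait remaining after PACU arrival in PACU-extubated patients. Three neostigmine-minus-sugammadex differences can be compared:
- Planned interval: (1 − pN)·wN + pN·L − (1 − pS)·wS − pS·L. Transport cancels.
- Until both in the PACU and extubated: planned + pN·RN − pS·RS. The added term is the omitted wait.
- Until extubation: the previous line + T·(pN − pS). This extra term arises because time to extubation excludes transport for OR-extubated patients and includes it for PACU-extubated ones.

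At L = 3, RN = 2.02 and RS = 0.17. At L = 5 both are 0.02. At L = 7 both are 0.00.

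| OR exit L | Shares N/S | Planned | In PACU and extubated | To extubation | Omitted wait |
|---|---|---|---|---|---|
| 3 | 30%/0% | 1.85 | 2.46 | 3.96 | 0.6 |
| 3 | 70%/10% | −0.65 | 0.75 | 3.75 | 1.4 |
| 3 | 50%/50% | 1.98 | 2.90 | 2.90 | 0.9 |
| 3 | 100%/100% | 0.00 | 1.85 | 1.85 | 1.85 |
| 5 | 30%/0% | 2.45 | 2.46 | 3.96 | 0.0 |
| 5 | 70%/10% | 0.55 | 0.56 | 3.56 | 0.0 |
| 7 | 30%/0% | 3.05 | 3.05 | 4.55 | 0.0 |
| 7 | 70%/10% | 1.75 | 1.75 | 4.75 | 0.0 |

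Worked row, L = 3 and 70%/10%: planned = 0.3 × 10.02 + 0.7 × 3 − 0.9 × 6.06 − 0.1 × 3 = −0.65. Omitted wait = 0.7 × 2.02 − 0.1 × 0.17 = 1.4. The further step to time to extubation is 5 × (0.7 − 0.1) = 3.0 minutes, all of it transport.

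Where shares are unequal, most of the gap between the planned figure and time to extubation is therefore transport counted in one group only. The wait itself largely overlaps with transport, a real saving that the planned interval records properly.

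**Sensitivity to when reversal is given.** A second model has no emergence time, OR exit possible at 2 minutes and transport of 4. With reversal at end of surgery and 50% PACU extubation in both groups:
- Planned: (14 + 6)/2 − (7 + 6)/2 = 3.5 minutes.
- In the PACU and extubated: (14 + 10)/2 − (7 + 6)/2 = 5.5 minutes.

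With reversal 5 minutes before end of surgery, the neostigmine wait ends at minute 5, before arrival at minute 6, and nothing is omitted. Over OR exits of 1 to 3 minutes and transport of 2 to 5, the omitted part is 0 to 2 minutes with the earlier reversal and 0 to 7 with reversal at end of surgery. The 7 arises only when everyone is extubated in the PACU, with OR exit at 1 minute and transport of 2.

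**The case for a change.** The strongest case for the concern is that the mechanism is real and needs no assumed numbers. A patient brought to the PACU intubated contributes an interval that no longer depends on the agent's minimum wait. The SAP states no purpose for the comparison, and with two different waits in the protocol a reader may take it as time saved by agent. If patients leave the OR early, the loss is not trivial even with equal shares: 1.98 against 2.90 minutes at 50%/50%. A label and a count of PACU extubations by agent would cost little.

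The mechanism stands, and so does the caution against reading the result as time to extubation. But the harm needs that reading, which the available documents do not make. It also needs early OR exit and a substantial PACU share after neostigmine, neither of which they report. Nor is the direction fixed. In the second model, with reversal at end of surgery and PACU extubation in half the sugammadex and none of the neostigmine patients, the planned difference is 7.5 minutes against 5.5 to extubation.

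The extra analyses are a matter of preference. An interval to extubation answers a different question and needs a recorded extubation time that the documents do not mention. Strata by place of extubation condition on something decided after reversal, so they are open to selection.

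**Conclusion.** No error. The interval can end before extubation in PACU-extubated patients, but the SAP says exactly where it ends, and following the plan gives a sound descriptive result for that quantity. On a consistent endpoint, the omitted wait is about 0 minutes when PACU-extubated patients leave the OR at 5 or 7 minutes. At 3 minutes it is 0.6 to 1.4 minutes for shares of 30%/0% to 70%/10%, and up to 1.85 if every patient is extubated in the PACU. These figures rest on assumed shares, emergence, exit and transport times, and on reversal at end of surgery. Other assumptions give anything from 0 to 7 minutes, so no size can be claimed for this trial.

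The conclusion rests mainly on the SAP's explicit definition of the interval. It would change only if the result were presented as time to extubation, recovery speed or the full time cost of an agent. Part of the protocol was not available, so this covers the visible text only. The SAP does not list the durations among its primary or secondary endpoints, and the residual-block analyses do not depend on them.

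### Does the comparison of time to PACU arrival by reversal agent need its own stated analysis set, given that the per-protocol exclusion could distort it?

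*SAP*

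**What the plan says.** The SAP's Statistical analysis section has two paragraphs. The first defines the primary endpoint and its interval: "The primary endpoint, incidence of PRNB (nTOFR <0.9) on arrival to the PACU, was calculated with exact binomial 95% confidence interval". It then calls the primary analysis per-protocol and adds that "patients were excluded if the protocol was not followed". The secondary endpoints, severe residual block on PACU arrival and residual block at extubation, follow with their method: "These were also calculated with the exact confidence intervals". Means with standard deviations, or frequencies, are specified for baseline characteristics.

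The second paragraph holds two comparisons of the time from end of surgery to PACU arrival. One contrasts "patients whose tracheas were extubated in the OR and those extubated in PACU". The other is the one at issue: "We also compared the duration between end of surgery and arrival to the PACU for patients receiving sugammadex or neostigmine". Neither has a stated analysis set, summary measure, test or interval.

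The Protocol section sets the waits: "The protocol calls for a minimum of 10 minutes after neostigmine administration and minimum 3 minutes after sugammadex administration before tracheal extubation".

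**The concern.** The exclusion sentence can be read narrowly, as part of the primary analysis, or broadly, as applying to the whole study. On the broad reading, and if a wait below the minimum counts as not following the protocol, a patient extubated 7 min after reversal is removed if given neostigmine and kept if given sugammadex. For a patient extubated in the OR, extubation comes before PACU arrival, so the wait will usually overlap the interval being compared. The exclusion would then select on a component of the outcome, with a different threshold in each group.

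Nor would it show what full adherence looks like, because the 7-minute neostigmine patient is deleted, not counted at 10 min. The neostigmine minus sugammadex difference would tend to come out too large, and some difference could appear where none exists. Readers may well use a time comparison between two drugs, so the question deserves a check.

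**Working it through.** **Inputs.** The cut-offs of 10 min (neostigmine) and 3 min (sugammadex) come from the Protocol section. The documents give no time data, number of patients per agent, number excluded or reasons for exclusion. The SAP states no figure for this comparison, so there is none to reproduce. Every distribution below is an assumption.

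**Step 1: general size.** Let a share q of OR-extubated neostigmine patients be excluded for a short wait, with mean waits m_ret (retained) and m_exc (excluded). The retained mean exceeds the all-patient mean by q(m_ret − m_exc). With assumed means of 14 and 7 min:
- q = 0: 0 min
- q = 0.1: 0.1 × 7 = 0.7 min
- q = 0.2: 0.2 × 7 = 1.4 min
- q = 0.3: 0.3 × 7 = 2.1 min

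**Step 2: same wait distribution for both agents, so the true difference is 0.** For a lognormal wait with median M and log SD s, the share below c is Φ(k), with k = ln(c/M)/s. The mean of those kept is M·exp(s²/2)·[1 − Φ(k − s)]/[1 − Φ(k)]. The artefact is this mean at c = 10 minus the same mean at c = 3.

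For M = 14 and s = 0.35, k = ln(10/14)/0.35 = −0.961, so 16.8% of neostigmine patients are excluded. The means of those kept are 16.20 and 14.88 min, a difference of 1.31 min. Other assumptions give:

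| Median (min) | Log SD | Neostigmine excluded | Artefact (min) |
|---|---|---|---|
| 16 | 0.20 | 0.9% | 0.07 |
| 14 | 0.20 | 4.6% | 0.24 |
| 15 | 0.30 | 9% | 0.7 |
| 16 | 0.35 | 9.0% | 0.83 |
| 14 | 0.35 | 16.8% | 1.31 |
| 12 | 0.35 | 30.1% | 2.00 |
| 12 | 0.50 | 36% | 3.4 |
| 6 | 0.70 | 77% | 7.4 |

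**Step 3: from the wait to the measured interval.** The wait starts at reversal, whereas the interval starts at end of surgery. Write the interval as D = R + T + X, where R is end of surgery to reversal (negative if reversal comes first), T is the wait and X is extubation to PACU arrival. If longer waits go with earlier reversal, part of the effect cancels. By simulation at median 14 and log SD 0.35, the 1.31 min becomes:
- SD of R 3 min, correlation of R with T −0.5: 0.86 min
- SD of R 5 min, correlation −0.5: 0.56 min
- SD of R 5 min, correlation −0.8: 0.10 min

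Patients extubated in the PACU dilute it further, because their wait ends after the interval has closed.

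**Step 4: do the two conditions hold?**
- *Does the exclusion cover this comparison?* The SAP attaches it to the primary analysis, which is an incidence of residual block. The time comparisons stand in a separate paragraph and describe their groups only by the agent received.
- *Was a short wait a reason for exclusion?* No list of excluding departures appears. The Protocol section's wording is graded: several items are recommended, providers were told to follow practice suggestions, the waits are called for, and only the tactile assessment before reversal is described as mandatory. Research staff also gave reminders, so q could be close to zero.

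Neither condition is established. If either fails, this artefact is zero.

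**The case for a change.** The strongest case for a change is that the omission is real, the direction of any bias is predictable, and a few sentences would close the gap: name the set, give a mean difference with an interval, and show the per-protocol result beside it with exclusions by agent and reason. If few patients were excluded for short waits, the two results would agree and readers could see that. A real difference in required waits does not answer the point either. At median 14 min and log SD 0.35, having every patient wait at least the minimum gives a difference of 0.27 min, against 1.31 min under exclusion.

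The omission, the direction and the arithmetic all stand. The need for a change does not. The no-difference example gives sugammadex patients the long waits of neostigmine patients, although the protocol builds in a 7-minute gap between the minimums (10 − 3); it shows what is possible, not what is likely here. Making all patients the main set is also a choice of question. The study evaluates a best-practice protocol, so times among patients managed by it are a legitimate target, and reasonable statisticians could prefer either set. Finally, the text shown describes no randomisation between agents. Confounding by choice of agent would remain whichever set is used, and a formal interval would not remove it.

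**Conclusion.** The SAP leaves out the analysis set and summary measure for this comparison, and it would have been clearer with them. The literal reading, patients who received either agent, is workable and free of the selection described. The distortion needs a broader reading of the exclusion sentence and an exclusion reason that the documents never state. Its size, from under 0.1 to about 7 min in the examples above, rests wholly on assumed waits and could be near zero.

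The comparison is unadjusted, has no stated hypothesis, is not among the listed primary or secondary endpoints, and has no bearing on the primary incidence or its exact interval. The SAP is already written in the past tense, so added wording would clarify reporting and would not be prespecification. This is a gap that an analyst fills sensibly by saying which patients were compared. No change to the plan follows. The conclusion would differ if short waits had been a common reason for exclusion among neostigmine patients and the comparison had been run only on those retained.

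### The sugammadex–neostigmine comparison of time to PACU specifies no adjustment and no random choice of agent is described, so block depth, case type or place of extubation could pass for an agent difference

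*SAP*

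**What the plan says.** The last paragraph of the SAP's Statistical analysis section contains two comparisons of the same duration. One is by place of extubation, operating room or PACU: "We compared the duration between end of surgery and arrival to the PACU for patients whose tracheas were extubated in the OR and those extubated" (the quotation stops just before the second place is named). The other is by reversal agent: "We also compared the duration between end of surgery and arrival to the PACU for patients receiving sugammadex or neostigmine". Neither comes with a test, model, covariate list, stratification or interval. The exact confidence intervals in that section belong to the PRNB incidences.

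The Protocol section of the protocol bears on how the two agent groups could differ:

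- Block is assessed before reversal: "At the end of the procedure, a tactile pre-reversal assessment of the thumb response to ulnar nerve stimulation was mandatory".
- Depth of relaxation is tied to the operation: the protocol recommends "intraoperative muscle relaxation according to surgical requirement".
- The waits before extubation differ by agent: "The protocol calls for a minimum of 10 minutes after neostigmine administration and minimum 3 minutes after sugammadex administration before tracheal extubation".

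Under Study procedures, depth was also measured quantitatively at that moment: "Additional measurements were obtained in duplicate immediately before reversal when the anesthesia provider made the tactile pre-reversal assessment". The SAP separately describes "baseline measures of patient and surgery characteristics". The supplied text does not say how the agent was chosen. Table 1, which may hold the rule, is not in the supplied text, and that absence is not a fault of the plan.

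**The concern.** The groups are formed by the drug received, and nothing supplied describes a chance mechanism behind it. The provider has just felt the twitch response when the agent is given, so depth may enter the choice. Depth is in turn linked to the operation, and both can plausibly affect how long a patient takes to leave the operating room. Place of extubation may matter too, since a patient taken to the PACU still intubated need not complete the wait before extubation within the measured interval.

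The difficulty arises under either kind of choice. If providers choose freely, the contrast is open to confounding by indication. If the assessment dictates the agent, the contrast is largely one between depths of block. Only a choice unrelated to the patient's state would avoid both.

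At stake is the interpretation of the only between-agent comparison in the SAP. A bare difference in minutes invites a reader to credit it to the drug. A quantitative pre-reversal reading was taken, yet the SAP does not specify its use here.

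**Working it through.** **What can be reproduced.** The documents give no sample size, standard deviation, effect size or significance level for this comparison, so there is no planned figure to reproduce. The only related figures are the two minimum waits, which differ by 10 − 3 = 7 min. They run from drug administration to extubation, whereas the outcome runs from end of surgery to PACU arrival. The 7 min is therefore not the expected difference in the outcome.

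**Step 1: size of the bias.** For a binary feature such as deeper block:

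bias in the crude difference = (difference between agents in prevalence of the feature) × (minutes the feature adds).

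Assume 40% of patients have deeper block, with sugammadex given to 70% of these and 20% of the rest. Then:

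- share given sugammadex = 0.4 × 0.7 + 0.6 × 0.2 = 0.28 + 0.12 = 0.40;
- deeper block among sugammadex patients = 0.28 / 0.40 = 0.70;
- deeper block among neostigmine patients = 0.12 / 0.60 = 0.20;
- imbalance = 0.70 − 0.20 = 0.50.

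| Minutes added by deeper block (assumed) | Bias at imbalance 0.50 |
|---|---|
| 3 | 1.5 min |
| 5 | 2.5 min |
| 8 | 4.0 min |

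Over a wider assumed range, an imbalance of 0.1 to 0.8 and an effect of 2 to 10 min, the bias runs from 0.1 × 2 = 0.2 min to 0.8 × 10 = 8.0 min. The sign reverses if deeper block goes with shorter times, or with the other agent.

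**Step 2: what the bias does to an interval.** Simulation with 4,000 replicates per setting, 150 patients, the agent pattern above, residual SD 6 min and a true advantage for sugammadex set arbitrarily at 7 min (all assumed):

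| Minutes added | Crude estimate | 95% CI coverage, crude | Estimate adjusted for depth | Coverage, adjusted |
|---|---|---|---|---|
| 3 | 5.5 min | 69% | 7.0 min | about 95% |
| 5 | 4.5 min | 35% | 7.0 min | about 95% |
| 8 | 3.0 min | 8% | 7.0 min | about 95% |

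The crude estimates equal 7 minus the bias in Step 1. Neither the bias nor the coverage depends on the choice of 7.

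**Step 3: what the bias does to a test.** Suppose the agent has no effect, the SD is 8 min, there are 50 patients per agent, and a two-sided 5% test is used (all assumed). The standard error is 8 × √(2/50) = 1.6 min. A bias of 2, 3 or 5 min is then 1.25, 1.875 or 3.125 standard errors, and the false-positive rate is 24%, 47% or 88%.

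**Limit of these figures.** Adjustment recovers the true value in Step 2 because the model contains one confounder, measured without error, with both agents used at both depths. If the assessment fully determines the agent, there is no overlap and adjustment cannot separate drug from depth.

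**The case against.** The strongest reply has four parts.

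*The SAP does not commit to a crude analysis.* This stands. A reader might infer that the comparison was planned as unadjusted, but the SAP names no method at all. The supportable statement is that no adjustment is specified.

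*No document says that the agent was chosen by depth.* This also stands. A reader might infer that deeper block led to one particular agent. The protocol requires the assessment but, in the supplied text, does not connect it to the choice. The link is plausible and undocumented, so the direction of any bias cannot be stated.

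*No causal claim is made.* The time comparisons are not among the named endpoints and carry no hypothesis, so a descriptive label might be enough. This stands in part. The label is needed, but a bare difference gives the reader no means of judging how far the groups differ. Tabulating depth and case type by agent supplies that, and an adjusted estimate adds to it where the data permit.

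*Adjustment may be impossible.* If a protocol rule set the agent, the groups may not overlap in depth. The SAP says of its per-protocol primary analysis that "patients were excluded if the protocol was not followed"; if the same exclusion applies to the time comparison, which is not stated, overlap would shrink further. This stands, and it is why the adjusted estimate must be conditional on overlap.

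**Conclusion.** The concern holds in a limited form. As written, the comparison can mix the agent with block depth, case type and place of extubation, because the agent groups are not described as randomised and no method is given to separate these. The illustrative bias is 1.5 to 4.0 min for an imbalance of 0.5 in a feature worth 3 to 8 min. None of these inputs is in the documents, so the figures show only that the bias could be material.

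Two stronger readings are not supported. The first sets the bias against the 7-minute gap between minimum waits and concludes that a known share of the agent effect would be lost. That gap belongs to a different interval, and for patients extubated in the PACU the wait need not fall inside the measured one. The second is that the study's main results are compromised. The primary and secondary endpoints are PRNB incidences and do not rest on this comparison. The change is worth making because it is cheap, not because the study's main question is at risk.

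**What to change.** Amend the SAP's Statistical analysis section as follows:

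1. Label the comparison by agent as non-randomised and exploratory, say how the agent was chosen, and state which patients are included.
2. Tabulate pre-reversal nTOFR (or tactile count), named surgery characteristics and place of extubation by agent.
3. Where both agents were used at overlapping block depths, report the difference in duration with a 95% CI from a regression on agent, pre-reversal depth and the named surgery characteristics, beside the crude difference. Set the rule for the overlap range without reference to the durations.
4. Show durations by agent within each place of extubation. Stratified display is preferable to a covariate here, because place of extubation is settled after the agent is given and may partly result from it.
5. Where there is no overlap, report the durations as those of two groups differing in block depth and draw no conclusion about the agent.

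The different waits before extubation form part of using each agent under this protocol. Adjustment for depth does not remove their contribution, and the report should say so.

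The cost is SAP wording, one table and one regression. The pre-reversal readings were already part of the study procedures. The downside is some loss of precision and possibly fewer patients in the overlap range.
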